## **9.2 Setting**

### **9.2.1 Study Population**

Patients with documented uterine fibroids and symptoms such as HMB who are therapy-naïve to Yselty® and who meet the criteria defined in the SmPC for prescription in the respective country. Patients will be enrolled after the decision to treat with Yselty® has been made, or as soon as possible after the start of Yselty® treatment, however, not longer than 3 months after treatment initiation. The decision to treat with Yselty® will not be influenced by study inclusion.

No further selection criteria except for inclusion and exclusion criteria outlined below should be applied. Based on examination of patient enrolment using progress reports on recruitment, a Steering Committee (see section 9.8.1) will provide recommendations regarding modifications to the study conduct that might be introduced to maximise recruitment.

Physicians should identify patients at high risk for osteoporosis or BMD loss according to the SmPC and relevant local guidelines. Such risk factors include a history of a low trauma fracture or other risk factors for osteoporosis or bone loss (such as chronic alcohol and/or tobacco use, strong family history of osteoporosis, low body weight, chronic kidney

---

 High risk patients will be identified by their treating physician as described in section 9.2.1.

disease, and overactive parathyroid gland), including those taking medications that may affect BMD (e.g., systemic corticosteroids, anticonvulsants). A more extensive reference list of risk factors is provided available as a stand-alone document in section 15.1.

### **9.2.2 Inclusion Criteria**

- Signed informed consent
- Females of reproductive age  $\geq 18$  years
- New users of Yselty® (not longer than 3 months after treatment initiation)
- Indication of moderate to severe symptoms of uterine fibroids

### **9.2.3 Exclusion Criteria**

- Patients who have ever used another GnRH antagonist (e.g., relugolix, elagolix) before enrolment
- Contraindications as per the approved SmPC
- Enrolment in a prior clinical trial with Yselty®
- Patients participating in an investigational program with interventions outside of routine clinical practice

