**Table 1 Estimated schedule for the Yselty® PASS**

	First Visit (Enrolment)	Baseline (Yselty® Treatment Start) 	Observation Time Points  (Months Since Yselty® Treatment Start)			
			12	24	36	48
Assessment of inclusion/exclusion criteria	X	–	–	–	–	–
Date of signed informed consent	X	–	–	–	–	–
Date of first Yselty® dose	–	X	–	–	–	–
Year of birth	X	–	–	–	–	–
Sex	X	–	–	–	–	–
Height/weight	X	–	–	–	–	–
Yselty® dosing regimen (100 mg without ABT, 100 mg with ABT, or 200 mg with ABT)	X	–	X	X	X	X
Medical history	X	–	–	–	–	–
Concomitant diseases	X	X				
Alcohol/nicotine/drug/stimulant consumption	X	–	X	X	X	X
Relevant prior medication	X	–	–	–	–	–
Relevant concomitant medication	X	–	X	X	X	X
BMD assessment, including absolute density values, z-score/t-score values, DXA scan date, anatomic site of DXA scan, machine type, imaging parameters, reference population used (if available)	X	–	X	X	X	X
Clinical evaluation (including weight, blood pressure, clinical assessment of fibroid)	X	–	X	X	X	X
Change in Yselty® dosing regimen, reasons for change	–	–	X	X	X	X
Reported adherence to prescribed treatment	–	–	X	X	X	X
Laboratory values  and date of laboratory assessment (if available)	X	–	X	X	X	X
Liver enzyme elevation events 	X	–	X	X	X	X
Bone fracture events 	X	–	X	X	X	X
Events of uterine endometrial adenocarcinoma and mammary gland adenocarcinoma	X	–	X	X	X	X

	First Visit (Enrolment)	Baseline (Yselty® Treatment Start) 	Observation Time Points  (Months Since Yselty® Treatment Start)			
			12	24	36	48
Mood disorder events 	X	–	X	X	X	X
Cardiac disorder events suggestive of potential QT interval prolongation	X	–	X	X	X	X
ECG findings indicative of QT interval prolongation, according to the physician's information	X	–	X	X	X	X
RMP targeted follow-up questionnaires on uterine endometrial and mammary gland adenocarcinoma, QT interval prolongation, exposure in pregnancy/pregnancy outcome, cases of elevated liver enzymes 			X	X	X	X
AEs, SAEs, ADRs, SADRs, special situations 	X	–	X	X	X	X
Premature discontinuation, including reasons 	–	–	X	X	X	X

1 Date of first visit (enrolment) and date of first Yselty® dose (baseline) may be the same, or the date of first Yselty® dose may be up to 3 months prior to first visit. For patients with first Yselty® treatment before enrolment, baseline data can be documented retrospectively at enrolment.

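### The exclusion for other GnRH antagonists is dated to enrolment, not to the first Yselty dose, so for women enrolled after first dose an on-treatment switch makes them ineligible

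*Protocol*

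**What the plan says.** Section 9.2.3 lists four exclusions. The first removes "Patients who have ever used another GnRH antagonist (e.g., relugolix, elagolix) before enrolment". The second reads "Contraindications as per the approved SmPC" and carries no date. The other two concern an earlier trial of Yselty and participation in an investigational program.

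Section 9.2.2 admits new users of Yselty "not longer than 3 months after treatment initiation". Sections 9.2.1 and 9.2.6 repeat that window and ask for enrolment as soon as possible once treatment has begun. Footnote 1 to Table 1 confirms that "the date of first Yselty® dose may be up to 3 months prior to first visit".

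The Table 1 row "Assessment of inclusion/exclusion criteria" is ticked under the first visit (enrolment) and has a dash under baseline (treatment start). For women already on treatment, the same footnote says that "baseline data can be documented retrospectively at enrolment". That allowance covers baseline data. It does not move the date at which eligibility is judged.

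Section 9.2.5 asks for consecutive enrolment and for a screening log that holds the reason for non-enrolment and the dosing regimen of each ineligible patient, so that selection bias can be evaluated.

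**The concern.** In a new-user cohort, eligibility should describe the woman before exposure starts. Sections 9.2.1 and 9.2.2 show that intent by describing the population as therapy-naïve and as new users. Prior use of another GnRH antagonist is a pre-treatment characteristic. Use that begins after the first Yselty dose is an outcome of Yselty treatment.

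Because the criterion is dated to enrolment, it treats the two alike for anyone enrolled after her first dose. Inclusion then depends on something that happened on treatment, and the time at risk of exclusion depends on how late each site enrols. Country is a planned stratum in section 9.7.2, so a difference in enrolment delay between countries could appear as a difference in early switching.

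At stake are the early part of objective II.e (regimen changes) and the reasons for discontinuation in section 9.3.4. For objective II.i, only those adverse reactions that end in such a switch or amount to a contraindication are at stake. An analysis plan cannot restore women who were never enrolled, so the wording has to be settled in the protocol.

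**Working it through.** The protocol gives no figure on this point, and the precision figures in Table 2 are not touched by it. The check is a comparison of time anchors.

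**Anchors**

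| Item | Date it refers to | Source |
|---|---|---|
| Start of exposure | First Yselty dose | Table 1, baseline column |
| Enrolment | At the decision to treat, or up to 3 months after first dose | 9.2.1, 9.2.2, 9.2.6 |
| Assessment of criteria | Enrolment visit | Table 1 |
| Other GnRH antagonist | Any time up to enrolment | 9.2.3 |
| Contraindications | Not stated | 9.2.3 |

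**Two women with the same history.** Both start Yselty on day 0 and move to another GnRH antagonist in week 8.

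- Woman A enrols on day 0. No other antagonist has been used by then, so she is eligible. Her switch is recorded under objective II.e.
- Woman B has her enrolment visit in week 10, inside the 3-month window. By then she has used another antagonist before enrolment, so she is excluded and her switch is not recorded in the cohort.

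The new-user criterion does not itself bar woman B: it sets a limit on time since initiation and does not require continuing use. The exclusion wording is what removes her.

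**Contraindications.** The words about enrolment stand only in the first criterion. A condition that arises between first dose and a late enrolment visit can exclude a woman only because the second criterion has no date and Table 1 places its assessment at enrolment. This limb is weaker. The protocol does not list the contraindications, so how often one could arise within 3 months cannot be judged from it.

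**Which outputs are reached.** Sections 9.1.2 and 9.7.3.3 restrict the primary endpoint to women treated for more than 12 months. A woman who has left Yselty within 3 months is not in that set, so losing her does not bias it. A woman who acquired a contraindication and still continued past 12 months would be an exception in principle. The protocol gives no basis for expecting a material number.

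**Size.** Let L be the share of women enrolled after first dose, and q the share of those who switch or acquire a contraindication before enrolment. The share of otherwise eligible initiators excluded is L × q, and the number excluded per 1,000 enrolled is 1,000/(1 − L × q) − 1,000. The protocol gives neither input, so the values below are assumptions that show only how the result moves.

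| L | q | L × q | Excluded per 1,000 enrolled |
|---|---|---|---|
| 0.25 | 0.01 | 0.0025 | 2.5 |
| 0.50 | 0.03 | 0.015 | 15.2 |
| 1.00 | 0.10 | 0.10 | 111.1 |

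The last row takes every woman as enrolled late and one in ten as excluded. It marks the edge of the assumed range and is not an estimate.

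**The case against.** The strongest reply is that this hardly matters in a study of long-term use, and much of it stands.

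- **Little follow-up is lost.** Under section 9.2.6, a woman without BMD decrease or osteoporosis has her final visit when she stops Yselty. Section 11.3 then collects events only up to 30 days after the last dose. Woman B would add mainly retrospective data.
- **The exclusions can be counted.** The screening log in section 9.2.5 records them, and section 9.7.4 acknowledges selection bias. The log does not bring these women or their outcomes back into the cohort.
- **SmPC status may mean status at prescribing.** Section 9.2.1 speaks of women who meet the SmPC criteria for prescription, which fits that reading. This weakens the contraindication limb. It does not help the first criterion, whose date is explicit.

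Two stronger readings are tempting, and the protocol does not support them.

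A reader might infer that early adverse reactions and discontinuations in general are screened out of late enrollers. They are not. Most trigger neither exclusion, and stopping Yselty without starting another GnRH antagonist does not trigger the first. Table 1 collects adverse events and reactions at the enrolment visit, and section 11.3 covers events under exposure that the patient reports.

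A reader might also size the loss as the share enrolled late times the mean delay divided by 12 months, for example 0.5 × 1.5/12 = 6.25%, or 1 × 3/12 = 25%, of year-1 outcomes. That formula gives the share of any constant-hazard outcome that falls before enrolment. It describes delayed entry, a separate issue that re-dating these criteria does not solve, and not the loss through them.

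**Conclusion.** The point holds in a limited form. As worded, the first exclusion selects women enrolled after first dose on an event that follows exposure, and nothing else in the protocol corrects this. The contraindication exclusion can do the same through its missing date and Table 1.

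The severity is minor. That rests on reach and not on a computed number: only women enrolled after first dose are affected, only those who switch to another GnRH antagonist or acquire a contraindication in that interval, and the affected outputs are exploratory and descriptive. Switchers leave the primary endpoint untouched. The size cannot be derived from the protocol, because it states neither the share enrolled after first dose nor the rate of such early events.

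**What to change.** In section 9.2.3, change the end of the first criterion to *before the first Yselty dose*, and add to the second *present at the date of the first Yselty dose*. In Table 1, add a note that these two criteria only are assessed as of the first-dose date. The other exclusions should still be judged at enrolment. A blanket re-dating would admit a woman who joined an investigational program between first dose and enrolment.

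Record a later switch or newly arising condition as an outcome or a reason for discontinuation. In the reports, state from the existing screening log how many initiators were not enrolled for these two reasons. This changes study eligibility only and has no bearing on any woman's treatment.

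The cost is a few words and one table note. The first-dose date is already collected (section 9.3.1), and section 6 plans data collection to start only in Q1/Q2 2026. The downside is that a few women with very short exposure and mainly retrospective data enter the cohort.

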### **9.2.4 Withdrawal**

In this observational study, withdrawal from the study is independent of the underlying therapy and will not affect the patient's medical care. Each patient can refuse to further participate or may withdraw from the study at any time and without giving a reason. If a patient wants to terminate the study participation, no further data will be collected. In case the patient does not agree that the so far collected study data can be further used, her data will be deleted from the study database and not be used for any study related analysis. This does not include safety data already captured in the MAH's safety database and data already included in interim analysis datasets and outputs, which will be kept. In case a patient would like to withdraw the consent given earlier, she should inform her doctor and the site should document the withdrawal in the electronic case report form (eCRF) as well as in the patient medical records.

Patients who discontinue prematurely will not be replaced.

### **9.2.5 Representativeness**

The non-interventional, prospective cohort design was chosen to reflect real-world characterization of patients with documented uterine fibroids and symptoms such as HMB treated long-term with Yselty®.

The patients documented in this study shall be selected by eligibility. The eligibility criteria have been selected to allow for a broad representation of patients within the study.

No further selection criteria except for inclusion and exclusion criteria should be applied. Patients should be enrolled consecutively in order to avoid any selection bias and to increase the likelihood of representativeness. Non-eligible patients (e.g., no informed consent signed) will not be included. In case a patient is not eligible, the reason for non-enrolment, together with the dosing regimen must be documented in the patient screening log file to evaluate a possible selection bias. It is planned that a minimum of 10% of the total sample size (see section 9.5) will be recruited from each country to increase the likelihood of representativeness. There is no patient limitation per site.

### **9.2.6 Visits**

The physician documents an initial visit, follow-up visit(s), and a final visit for each patient in the electronic data capture (EDC) system. Follow-up visit(s) are documented as they occur per routine practice or physician's decision. The study protocol does not define exact referral dates for those visits. The expected schedule of the conduct of this study as per routine clinical practice is shown in Table 1. More than 1 visit per year can be recorded in the eCRF.

#### **Enrolment/Baseline**

Once a patient is found eligible for inclusion, the physician will inform the patient about the study. This will include discussing the consent form and asking the patient to read and – when agreeing to participate – sign the informed consent. Patients will be enrolled after the decision to treat with Yselty® has been made, or as soon as possible after the start of Yselty® treatment, however, not longer than 3 months after treatment initiation. Information will be collected by reviewing the patient medical records, if available, or during the clinical examination as shown in Table 1.

#### **Follow-up visit(s) during treatment**

Follow-up visits will be carried out during regular clinical practice visits until study completion. In this patient population, regular clinical practice visits are expected about every 12 months after Yselty® treatment start (see Table 1).

#### **Follow-up visit(s) for patients who experienced BMD decrease or osteoporosis during the study**

Patients who discontinued treatment with Yselty® but had BMD decrease or osteoporosis during the study should be observed in the study for up to 24 months after the last administration of Yselty®. Documentation of further visits by the physician during the further follow-up period will be limited to BMD assessments and relevant concomitant medications. For AE reporting please see section 11.3.

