### 9.1.2 Endpoints

The primary endpoint of objective **I**. is only assessed in patients with long-term treatment (>12 months) and is:

- Number and proportion of patients with a lumbar spine, total hip, or femoral neck BMD z-score below the threshold of -2 standard deviations.

The exploratory endpoints of this study are:

- For objective **II.a**:
  - Incidence rate of osteoporosis or fractures suspected to be due to osteoporosis; all suspected osteoporotic fractures (minimal- or non-traumatic) of long bones or spine where the physicians suspect an osteoporotic cause of the fracture
- For objective **II.b**:
  - Number and proportion of patients with elevated liver enzyme levels above the upper limit of normal
  - Incidence rate of adverse events suggestive of liver injury or related to liver enzyme elevation
- For objective **II.c**:
  - Incidence rate of adverse events regarding mood disorders including mood swings, affect lability, emotional disorder, irritability, mood altered, anxiety, bipolar disorder, mania, depression, depressed mood
- For objective **II.d**:
  - Incidence rate of uterine endometrial adenocarcinoma events
  - Incidence rate of mammary gland adenocarcinoma events

---

Additional analyses on ADRs will be performed.

 The RMP (see section 15.1) contains targeted follow-up questionnaires for these events. Physicians who report these events will be asked to fill the corresponding targeted follow-up questionnaire.

 The RMP (see section 15.1) contains targeted follow-up questionnaires for these events. Physicians who report these events will be asked to fill the corresponding targeted follow-up questionnaire.

 A list of MedDRA terms for hepatic events is available as a stand-alone document (see section 15.1).

- For objective **II.e**:
  - Number and proportion of patients starting each Yselyt® dosing regimen, time spent on each dosing regimen, and changes in dosing regimens
- For objective **II.f**:
  - Patient adherence to prescribed treatment, including ABT
- For objective **II.g**:
  - Incidence rate of adverse events for cardiac disorders (ventricular arrhythmias [e.g., ventricular tachycardia and ventricular fibrillation, flutter, torsade de points], cardiac arrest, and sudden cardiac death) suggestive of potential QT interval prolongation

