  - Incidence rate of adverse events regarding electrocardiogram (ECG) findings indicative of QT interval prolongation, according to the physician's information
- For objective **II.h**:
  - Frequency of use of DXA scans in defined time periods:
    - Among patients with >1-year treatment, the number and proportion of Yselyt® users who received at least 1 DXA scan between 10 months until 14 months
    - Among patients with >2-year treatment, the number and proportion of Yselyt® users who received at least 2 DXA scans between 10 months until 26 months
    - Among patients with >3-year treatment, the number and proportion of Yselyt® users who received at least 3 DXA scans between 10 months until 38 months
    - Among patients with ≥4-year treatment, the number and proportion of Yselyt® users who received at least 4 DXA scans between 10 months until end of study
  - Frequency of DXA scans prior to treatment initiation in patients at high risk for osteoporosis or bone loss

---

 Additional analyses on ADRs will be performed.

 The RMP (see 15.1) contains targeted follow-up questionnaires for these events. Physicians who report these events will be asked to fill the corresponding targeted follow-up questionnaire.

 The RMP (see 15.1) contains targeted follow-up questionnaires for these events. Physicians who report these events will be asked to fill the corresponding targeted follow-up questionnaire.

 High risk patients will be identified by their treating physician as described in section 9.2.1.

- Number and proportion of patients who received Yselty® at a dose of 200 mg for more than 6 months without concomitant prescriptions for ABT at suitable time periods (e.g., 3-month intervals)
- For objective **II.i**:
  - Incidence rate of ADRs
  - Incidence rate of SADR
- For objective **II.j**:
  - Mean absolute and relative change in density (g/cm^2) and absolute value and relative change of BMD z-score and t-score from baseline (for patients with baseline DXA scan as per routine clinical practice – per SmPC only recommended for patients at high risk for osteoporosis or bone loss)

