### **Final visit/End of observation period**

The final data collection (last visit) is at the end of study (regular end of study or after further follow-up for patients with BMD decrease or osteoporosis) or at discontinuation of Yselyt® therapy for patients without BMD decrease or osteoporosis (whatever is earlier). At this final observation point, the patient's condition and a treatment assessment will be documented as a follow-up visit with additional information on:

- Regular end of observation, or
- End of observation after further follow-up for patients who discontinued Yselyt® treatment but had a BMD decrease or osteoporosis (see section above) during the study, or
- Discontinuation of follow-up with the reason for discontinuation (e.g., end of therapy with Yselyt® and no BMD decrease or osteoporosis).

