2 This is the expected visit schedule, however, visits are to be performed as per routine practice. Additional visits can also be recorded. In case the observational period per country is prolonged, data collection will be prolonged as well.

3 Laboratory values include 25-hydroxy vitamin D, if available, and liver enzyme levels or values indicative of liver injury such as ALT, AST, bilirubin, GGT, and ALP, if available.

4 A list of MedDRA terms for hepatic events is available as a stand-alone document (see section 15.1) and will be further specified in the SAP.

5 Including events of osteoporosis or fractures suspected to be due to osteoporosis; all suspected osteoporotic fractures (minimal- or non-traumatic) of long bones or spine where the physicians suspect an osteoporotic cause of the fracture.

6 Including events of mood swings, affect lability, emotional disorder, irritability, mood altered, anxiety, bipolar disorder, mania, depression, depressed mood.

7 The RMP (see section 15.1) contains a targeted follow-up questionnaire for events indicative of uterine endometrial and mammary gland adenocarcinoma, QT interval prolongation, exposure in pregnancy/pregnancy outcome, and cases of elevated liver enzymes. Physicians who report an event indicative of these events will be sent the appropriate targeted follow-up questionnaire.

8 In case of discontinuation, AEs, SAEs, ADRs, SADRs, and special situations have to be documented as outlined in section 11.3.

9 Special situations include drug interactions, medication abuse, medication misuse, medication overdose, medication errors, unexpected therapeutic or clinical benefit from product use, pregnancy or lactation exposure with the product, lack of efficacy, off-label use, and occupational exposure (see section 11.4).

10 Physicians should continue to document BMD measurements during the extended follow-up period for patients who experienced BMD decrease or osteoporosis during the study. Management of AE/ADR occurring after treatment discontinuation will be managed in accordance with section 11.3.

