#### **9.7.3.3 Analysis of Primary Endpoint**

The primary objective will only be assessed in users with the long-term treatment (>12 months) and where z-scores of lumbar spine, total hip, or femoral neck are available. For rates of events of BMD z-scores below the age-related threshold of -2 standard deviations, the number and percentage of patients with these events will be provided including 95% CIs.

The aggregated number, frequency of DXA scans, anatomic site of DXA scan, machine type, and imaging parameters of DXA scans during the observational period will be analysed by descriptive statistics. If results of DXA scans can be interpreted in a categorised way, shift tables for the change from baseline, will be provided, where available. If images of the DXA scans can be provided by the doctors, they will be reviewed by 1 independent expert for their suitability and included in an additional sensitivity analysis.

Sensitivity analyses using different criteria (e.g., machine type) to select DXA scans that ensure their comparability will be performed to evaluate the primary endpoint if the sample size allows (e.g., if more than 30 patients remain after selection of suitable cases) and will be further detailed in the SAP.

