### **11.3 Documentation**

All AEs under exposure to Yselty® that have been reported by the patient to the physician (i.e., AEs, SAEs, ADRs, SADR, special situations) will be documented on the AE Report form in the eCRF/EDC system. Assessment on seriousness and relationship to product, treatment duration, action taken, and outcome of the event will be provided by the treating physician, who will also be responsible for following up on the outcome of SAEs, if this information is not available when first reported. Where required, physicians might be contacted directly, per the MAH's internal follow-up procedure, to obtain further information.

In addition, for selected events (see section 9.4), the MAH will utilise the targeted follow-up questionnaires, where applicable, as per the latest version of the RMP (see section 15.1). The purpose is the ongoing monitoring and safety evaluation of these events.

The documentation of any event within the eCRF ends with the completion of the follow-up of the patient or until it is no longer possible (e.g., lost to follow-up, death, withdrawal). In case of discontinuation of Yselty® for any reason, all events will be collected that occurred up to 30 days after the last administration. Since the  $t_{1/2}$  elimination time of linzagolix is 15 hours, exposure has well ended after 30 days. However, patients who discontinued treatment with Yselty® but experienced BMD decrease or osteoporosis during the study will continue to be followed up unless they have completely withdrawn from the study, and all AEs associated with BMD loss (e.g., osteoporosis, osteopenia, fractures) and all ADRs will be collected irrespective of treatment discontinuation.

All AEs will be summarised in tabulated forms in the interim safety analysis and final study report.

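### The trigger for off-treatment follow-up (BMD decrease or osteoporosis) is not tied to the primary endpoint, so a woman with a z-score below -2 on her only scan may be closed out when she stops Yselty

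*Protocol*

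**What the plan says.** **Who is followed after stopping.** Section 9.2.6 covers women who have stopped taking the drug. It says that those who "had BMD decrease or osteoporosis during the study should be observed in the study for up to 24 months after the last administration". The final-visit paragraph of the same section places the last data collection at discontinuation of Yselty "therapy for patients without BMD decrease or osteoporosis (whatever is earlier"). Table 1, footnote 10, repeats the trigger: "Physicians should continue to document BMD measurements during the extended follow-up period for patients who experienced BMD decrease or osteoporosis during the study". So does section 11.3 for adverse events, where patients who stopped "but experienced BMD decrease or osteoporosis during the study will continue to be followed up unless they have completely withdrawn from the study". For everyone else who stops, section 11.3 says that "all events will be collected that occurred up to 30 days after the last administration". The off-treatment subgroup analysis in section 9.7.3.4 is defined by BMD decrease.

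**What the primary endpoint is.** Section 9.1.2 gives it as "Number and proportion of patients with a lumbar spine, total hip, or femoral neck BMD z-score below the threshold of -2 standard deviations". Section 9.7.3.3 assesses it in women treated for more than 12 months "where z-scores of lumbar spine, total hip, or femoral neck are available". No earlier scan is needed.

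**Who has an earlier scan.** Section 9.1.2 notes that a baseline DXA is "per SmPC only recommended for patients at high risk" of osteoporosis or bone loss. The Abstract (Variables) says the same. The first on-treatment scan window in section 9.1.2 is 10 to 14 months.

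**The concern.** The endpoint is a level that one scan can establish. The follow-up trigger is a change, which needs two scans, or else a diagnosis of osteoporosis. None of the four places that state the trigger mentions a z-score below -2.

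Consider a woman with no baseline scan, a z-score of -2.4 at her first scan after more than 12 months of treatment, and no osteoporosis diagnosis. She is a primary-endpoint case, yet her record shows no decrease. If she then stops Yselty, the final-visit rule read literally ends her data collection. Her later BMD values would not be documented, and bone events would be collected for only 30 days after the last dose.

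The trigger is also loose in the other direction. BMD decrease has no stated amount, site, comparator scan or assessor. A woman with two scans and any fall qualifies on a literal reading, even if the fall is within measurement error.

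This cannot be left to the SAP. The trigger decides at the site whether visits are documented, and an analysis plan finalised before database lock cannot recover visits that were never recorded.

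**Working it through.** **1. Texts side by side**

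| Place in protocol | Criterion | Scans needed |
|---|---|---|
| 9.1.2 and 9.7.3.3, primary endpoint | z-score below -2 at any of three sites, more than 12 months of treatment | One |
| 9.2.6 follow-up, 9.2.6 final visit, Table 1 footnote 10, 11.3 | BMD decrease or osteoporosis | Two, or a diagnosis |
| 9.7.3.4, off-treatment subgroup | BMD decrease | Two |
| 9.9, limitations | Treats a z-score below -2 as a sign of bone loss | One |

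Section 9.9 is the only place that links the threshold to loss. Section 9.5 calls the same threshold a cutoff for low bone density. A site could therefore keep the woman described above or close her out, and cite the protocol either way.

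**2. The plan's own figures (section 9.5, Table 2)**

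Effective N = 1,000 x 0.8^k gives 800, 640, 512 and 409.6 at 12, 24, 36 and 48 months. The half-width is 1.96 x sqrt(0.025 x 0.975 / N), which gives 1.08%, 1.21%, 1.35% and 1.51%. These agree with Table 2 after rounding, so its inputs can be used here.

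**3. Size of the gap**

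- Expected below -2 at 12 months if every remaining patient is scanned: 800 x 0.025 = 20.
- The protocol gives neither the share scanned nor the share without an earlier scan. Assumed ranges: 30% to 100% scanned; 50% to 90% of these without an earlier scan.
- Positive on the only scan, low end: 800 x 0.30 x 0.025 x 0.50 = 3.0.
- Positive on the only scan, high end: 800 x 1.00 x 0.025 x 0.90 = 18.0.
- Only those who stop before a second scan are exposed. With the protocol's 20% yearly dropout as a stand-in for stopping Yselty: 3.0 x 0.20 = 0.6 to 18.0 x 0.20 = 3.6 women in the following year.

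**4. Sensitivity to the 2.5%**

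Section 9.5 takes the lowest of three sites, and section 9.9 concedes that more sites raise the chance of a value below threshold. If the three z-scores are standard normal with a common correlation of 0.7 (an assumption), the proportion is 5.0%, or 40 of 800, and every count in step 3 doubles. The order of magnitude stays the same.

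**The case against.** **Exit is not certain.** A reader might infer that every such woman leaves the study on stopping. The protocol does not say so. BMD decrease is undefined, section 9.9 reads a z-score below -2 as bone loss, and a physician may diagnose osteoporosis. This stands: the supportable statement is that she may be closed out, depending on the site.

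**The primary endpoint is untouched.** This also stands. Her case is counted before she stops, and no listed objective concerns recovery after stopping. The off-treatment BMD data feed one exploratory subgroup.

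**A documented fall is a defensible focus.** The protocol's 2.5% is a reference-population figure, so 20 women below -2 is what would be expected with no drug effect. One low value does not show loss on treatment, and later values cannot be read as recovery from it. That is a reason to report these women separately. It is a weaker reason not to document them, since they are the cases the primary endpoint flags.

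**The numbers are easily overstated.** A reader might take 18 as the number lost. That assumes that all are scanned and ignores that only women who stop before a second scan are exposed. Baseline scans also go to high-risk women, who are probably more often below -2, so cases may have an earlier scan more often than average. Against that, stopping may be more likely after a low result than the 20% suggests. Both are inferences.

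**The section 9.7.3.4 subgroup.** A reader might infer that its fracture results are distorted, or that it consists mostly of high-risk women. The text supports neither. It lists only z- and t-scores for this subgroup, and annual scans give longer-term users of any risk level a second scan. Its comparability conditions (same machine type and location, at least 6 months apart) govern the analysis of changes, not the site's decision to keep a patient.

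**Conclusion.** The point holds as a mismatch between the observation trigger and the primary endpoint, made worse by an undefined term. It is not a certain loss of patients and not an error in the primary analysis. What is at risk is off-treatment BMD, and bone events beyond 30 days after the last dose, for women who met the primary endpoint on their only scan and have no osteoporosis diagnosis. The estimate is about 0.6 to 3.6 women in the year after the 12-month scan. It rests on the protocol's 800 and 2.5%, on assumed shares for scanning and for no earlier scan, and on 20% dropout standing in for stopping. That is few women, but only about 20 cases are expected at 12 months. Severity is minor to moderate, and the change is a cheap improvement.

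**What to change.** - In section 9.2.6 (the follow-up and final-visit paragraphs), Table 1 footnote 10 and section 11.3, add to the observation trigger any on-treatment z-score below -2 at lumbar spine, total hip or femoral neck. This is slightly wider than the endpoint, which is limited to more than 12 months of treatment.
- Define BMD decrease once, as a fall between comparable scans that exceeds measurement error, and use that definition in all these places and in section 9.7.3.4.
- In section 9.7.3.4, report women who enter only through the z-score criterion as a separate off-treatment group, and say that without an earlier scan their later values do not measure recovery from a documented loss.

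The cost is protocol and eCRF wording, plus off-treatment documentation for a few extra patients. Only routinely available data are recorded, so no scan and no treatment rule is added.
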